Home-based yoga is a very attractive solution to address problem of access. The successful implementation of teleyoga could advance and elevate the treatment of AD and

caregivers. To date, only two small studies have examined the feasibility of at-home teleyoga involving patients with COPD (55) or cancer (56). Both studies reported negative experiences with the technology, and both concluded that internet-based yoga could be feasible if the technology was simplified.

Objectives

Specific Aims and Hypothesis

Specific Aims:

1. Modify an existing teleyoga intervention to use with AD patients and their caregivers and address the technical challenges of at-home teleyoga.
2. Demonstrate the feasibility of conducting group teleyoga with AD patients and their caregivers.

Hypothesis 1 (primary): It will be feasible to maintain an a priori adherence to $\geq 75\%$ classes.

Hypothesis 2 (secondary): Treatment satisfaction as measured by the Multi-Dimensional Treatment Satisfaction Measure will be neutral or positive for all factors.

Study Design

No randomization into treatment groups will be needed in this study. The study involves the development of the technical methods and yoga protocol design needed to deliver at-home yoga instruction via videoconferencing.

Recruitment: 15 dyads (pairs of Alzheimer's disease patients and their caregivers) with chronic musculoskeletal pain will be recruited through different streams such as flyers posted at Stanford Alzheimer's Disease Research Center, and VAPAHCS Pain Clinic. We may also ask VA providers to refer their patients with chronic pain, contacting organization that provide guidance and support for people with Alzheimer's disease or chronic pain, web-based advertising, local advertising, social media advertising (Facebook, Twitter and Instagram using Web Based Recruitment Text, and mass-mailings to potential participants who may meet study eligibility criteria. To recruit AD patients, we may also use Brain Health Registry, which is a web-based platform run by UCSF to match patients with AD with suitable clinical trials (<https://www.brainhealthregistry.org/for-investigators>). The BHR will send our study information to interested prospective participants. These materials are attached to Tab 16 and include a BHR study description, BHR initial email invitation, BHR first follow-up email, and BHR second follow-up email.

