and post-treatment), we will estimate how they change over time (pre to post). Note that some of the assessment measures used are used only for AD patients or caregivers. The results will be reported for both groups separately. Accordingly, in terms of AD patient outcomes, we will estimate changes in pain (DVPRS), depression (BDI-II), sleep (PSQI) and cognition (CanTab). These results will provide preliminary data on target engagement and therefore will inform and shape the future trial in terms of elucidating the mechanism of action. For the caregiver measures, we will estimate changes in caregiver burden (Revised Memory and Behavior Problems Checklist), quality of life (SF-36), depression (BDI-II), and sleep (PSQI). We will also explore the relationship between changes in patient outcomes and their caregiver outcomes. For all analyses regarding changes in outcomes, we will first employ simple paired t-test (pre vs. post) given the correlation between pre and post measures. We will also estimate changes based on longitudinal mixed effects modeling using maximum likelihood estimation. We will put in rigorous effort to minimize missing data. Nonetheless, we expect some attrition by post intervention assessment. In our mixed effects modeling, data points that are missing due to attrition or missing assessment will be handled assuming that data are missing at random conditional on observed information. In all statistical analyses, we will focus on collecting preliminary data on clinical significance (i.e., effect size) instead of making formal inference (i.e., p-value).

Inclusion/Exclusion Criteria

Inclusion Criteria for AD patients (As determined by):

- Diagnosis of probable Alzheimer's disease- Baseline
- Mini-Mental State Examination (MMSE) score 18-25 (Mild AD) (screening interview) \geq 18 years old
- Has a primary care provider who can provide medical clearance for participation in the study
- Diagnosis of chronic musculoskeletal pain $>$ 6 months
- Minimum pain intensity at screening visit: pain rated \geq 4 on a 0-10 Numeric Rating Scale (NRS)
- Not begun new pain treatments or medications in the past month
- If on a psychotropic medication regimen: stable regimen for at least 4 weeks prior to entry to the study; willingness to remain on a stable regimen during the 12-week acute treatment phase
- English literacy
- Wireless internet connection at home (Screening interview)

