- Has a caregiver who is willing to accompany AD patient for treatment, and who can receive yoga treatment at the same time as AD patient.

Exclusion Criteria for AD patients (As determined by):

- Participation in another concurrent clinical trial
- Back surgery within the last 12 months

- Back pain potentially attributed to a specific underlying cause, disease, or condition (VA EMR; screening interview)
- Baseline pain <4 or ≥9 on a 0-10 Numeric Rating Scale (NRS)

Inclusion Criteria for CAREGIVERS of AD patients (As determined by):

- Are caring for a patient diagnosed with AD who will practice yoga together with them
- Has a primary care provider who can provide medical clearance for participation in the study (Yoga Medical Clearance Form)
- Exclusion Criteria for Caregiver
- Participation in another concurrent clinical trial
- Attended or practiced yoga ≥ 1 x in the past 12 months
- Attended or practiced yoga ≥ 1 x in the past 12 months

Informed Consent Process

Participants will be recruited from four sources: Brain Health Registry, the VAPAHCS Pain Clinic, local advertising, and web-based advertising. These sources will result in either 1) the potential participant calling the study team or 2) with the participant's consent, the study staff contacting them directly. Study candidates will be invited to VAPAHCS for a screening visit, during which the Project Manager will obtain informed consent and review the Health Insurance Portability & Accountability Act (HIPAA) document.

The informed consent process will involve the AD patient and their caregiver together. They will complete separate consent forms. As we are enrolling AD patients with impaired consent capacity, the caregiver will act as a legal authorized representative (LAR) and provide consent for the AD patient, who will be asked to provide their assent. These forms will include the HIPAA document and are estimated to take about 60-90 minutes. It will take place in a quiet office or interview room, located in the same building as the PI, who will be available to answer any of the study candidate's questions.

1. The Project Manager will explain the information contained in the written informed consent forms (purpose, procedures, risks, benefits, alternatives to participation, etc.) and HIPAA documents to the study candidates verbally, in lay language.

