 - a. The Project Manager will check for comprehension, allow the study candidates ample opportunity to ask questions throughout the process, and repeat the information, as necessary.
 - b. Care will be taken to inform the study candidate that their participation is entirely voluntary, and they may withdraw at any time and for any reason without penalty or loss of benefits to which they would otherwise be entitled.
 - c. Study candidates will then be asked to carefully read the informed consent form to consider whether or not to participate in the research and to ask questions.

- d. To ensure that the study candidate understands the research, they will next be asked to summarize the consent form and HIPAA addendum, with a special focus on the discomforts, risks, benefits, and confidentiality sections.
2. If the study candidate demonstrates (by stating in his/her own words) an understanding of the purpose, risks, and benefits of the study and agrees to participate in the study, he/she will be asked to initial each page, in addition to sign and date the last page of the consent form and the HIPAA document.
3. The Project Manager who oriented and obtained informed consent will sign and date the informed consent form.
4. The Project Manager will provide each enrolled participant with a photocopy of the original signed copy and keep the original signed copy in a binder in a locked cabinet.

The emphasis on the voluntary nature of participation is designed to minimize the possibility of coercion or undue influence on participation. The study candidate will be given time to understand the written informed consent form and make an informed decision. All treatments for this study will be provided in group formats, so potential participants will be reminded that full anonymity cannot be maintained. Following the informed consent process, the enrolled participant will complete other measures (See Research Strategy).

Screening Procedures

Potential participants (n=15) will be screened via phone. The Project Manager will obtain informed consent and review the Health Insurance Portability & Accountability Act (HIPAA) document. After obtaining informed consent, a trained researcher will collect demographic information (Demographic Questionnaire). Screening for protocol eligibility for AD participants will include the MMSE, PEG, DVPRS and Clinical DVPRS.

Study Assessments

Demographics Questionnaire: Documents age, gender, education, and race/ethnicity.

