Clinical Questionnaire: Self-report document focusing on the existence of 78 health symptoms taken from a list of ICD-9 codes that are highly likely to represent chronic pain.

Medication Use: Self-report of all current pharmacological and non-pharmacological treatments.

Yoga Home Practice Log: Log for participant to document their yoga home practice on non-treatment days.

BDI-II Beck Depression Inventory-II (BDI-II): Contains 21 self-report questions, scored on a 0-3 scale, related over the past two weeks to sleep, appetite, punishment, suicide, and interest in sex.

Brief Pain Inventory-Short Form (BPI-SF): Assesses intensity and impact of pain on functioning on a 0-10 rating scale. Interference is assessed on daily life (general, walking, work, mood, enjoyment, relationships, sleep). The BPI is recommended by the Initiative on Methods, Measurement, and Pain Assessment in Clinical Trials (IMMPACT) group for inclusion in clinical trials evaluating pain.

Defense and Veterans Pain Rating Scale (DVPRS): A five-item scale: one 0-10 pain intensity numeric rating scale and four supplemental items measuring functional outcomes (general activity, sleep, mood, level of stress). The pain intensity scale is designed to improve upon

existing scales by using visual cues and word descriptors to anchor pain ratings with perceptual experiences and limitations imposed by pain.

PEG: A 3-item pain measure derived from the Brief Pain Inventory and validated in ambulatory care settings. It includes 1 severity item (average pain) and 2 interference items (enjoyment of life and general activity).

Pittsburg Sleep Quality Index (PSQI) (62): Contains 10 self-report questions regarding sleep habits over the past month, including discrete responses (e.g. amount of sleep) and responses scored on a 0-3 scale (“not during the past month” to “three or more times per week”), related to sleep quality, medication use, motivation, and fatigue. A global sum score indicates level of sleep difficulties.

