Consent Form	×			
Demographic Questionnaire	×			
Clinical Questionnaire	×			
Yoga Medical Clearance Form	×			

Medical Use		x		x
Yoga Home Practice Log			x	
Mental Health				
BDI-II		x		x
Pain/QOL/Physical				
BPI-SF		x		x
DVPRS	x			
PEG	x	x		x
PROMIS-PI		x		x
Behavioral				
Treatment Satisfaction				x
Provider Suggestions				x
Patient Safety			x	x
Treatment Fidelity			x	

Table 2. Study Measures and Timetable of Data Collection

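### Does printing the 12-month yoga exclusion twice for caregivers, and not at all for AD patients, undermine the feasibility results?

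*Combined protocol and SAP*

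**What the plan says.** The section Inclusion/Exclusion Criteria has separate lists for AD patients and caregivers. Under the caregiver exclusion heading, "Attended or practiced yoga ≥ 1 x in the past 12 months" is printed on two consecutive lines. The list headed "Exclusion Criteria for AD patients (As determined by)" has four entries: concurrent trial, recent back surgery, back pain with a specific cause, and baseline pain outside a range. None concerns past yoga. The patient inclusion list mentions yoga only to require a caregiver who can be treated alongside the patient. Its nearest related entry is "Not begun new pain treatments or medications in the past month".

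Under Screening Procedures, "Screening for protocol eligibility for AD participants will include the MMSE, PEG, DVPRS and Clinical DVPRS". Under Study Assessments, the Medication Use form is a "Self-report of all current pharmacological and non-pharmacological treatments", which Table 2 appears to place at baseline and post-treatment. Table 2 also lists a "Yoga Medical Clearance Form" at screening, whose contents are not described.

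The primary hypothesis reads "It will be feasible to maintain an a priori adherence to" at least 75% of classes. The secondary hypothesis concerns treatment satisfaction. Study Design describes 15 dyads, 12 weekly classes, no randomisation and no power for efficacy.

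**The concern.** The protocol treats a single session in 12 months as enough to exclude a caregiver, yet as printed it sets no such limit for the patient, whose pain, mood, sleep and cognition are analysed before and after treatment. The consecutive duplicate invites the suspicion that one copy belongs in the patient list. The Background says yoga use is rising among AD patients, so candidates with experience can be expected.

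The described forms do not obviously fill the gap. Medication Use covers current treatments, and the one-month rule covers newly started ones. Yoga that a patient stopped some months ago, or does not regard as treatment, falls outside both. If experienced patients attend or rate the classes differently from novices, the adherence and satisfaction figures carried into the next trial would describe a mixed group, and the report might not say so.

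**Working it through.** **1. The text.** Occurrences of the 12-month line: caregiver exclusions 2, patient exclusions 0, patient inclusions 0. Described forms with a 12-month yoga question for patients: 0. These facts are correct.

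**2. What the layout can prove.** In the same section the caregiver exclusion heading is itself printed as a bullet among the caregiver inclusions, and the patients' MMSE and age criteria run together on one line. In lists with such flaws, a repeated line is weak evidence that a criterion was moved from elsewhere. No other statement ties prior yoga to patient eligibility.

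**3. What the silence of the forms can prove.** Apply the same test to other criteria. No described form asks about back surgery, concurrent trials, English literacy or home internet. None asks the caregiver's own yoga question, although that exclusion is explicit. Some criteria are assigned elsewhere, as in "Back pain potentially attributed to a specific underlying cause, disease, or condition (VA EMR; screening interview)", and the contents of the screening interview are not given. The four screening instruments are introduced as things screening will include, which is not an exhaustive list. The silence is therefore general, and it does not show that patients' yoga history goes unrecorded.

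**4. How many patients might be affected (illustration).** The Background gives yoga use of about 25% in neurological conditions including AD and about 17% in people without such conditions, with no look-back period. If these rates applied to the 15 patients:

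- Expected prior users: 15 × 0.17 = 2.55 and 15 × 0.25 = 3.75.
- Chance of at least one: 1 − 0.83^15 = 0.939 and 1 − 0.75^15 = 0.987.

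These are not bounds. A patient who practises with the caregiver is excluded indirectly through the caregiver. On the other side, the Background also cites 41% for use of complementary practices including yoga in musculoskeletal pain.

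**5. Effect on adherence (illustration).** Assume adherence is the mean share of 12 classes over 15 patients, so the target is 0.75 × 12 = 9 classes. With k prior users who each attend d classes more or fewer than the others, the all-patient mean differs from the non-user mean by (k/15) × (d/12).

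| d (classes) | k = 1 | k = 4 |
|---|---|---|
| 1 | 0.6 points | 2.2 points |
| 3 | 1.7 points | 6.7 points |

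For scale, the largest entry is 4 × 3 = 12 class attendances out of 15 × 12 = 180. That equals the effect of one patient attending no classes instead of all 12.

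**6. A deliberately extreme case.** If the all-patient mean were exactly 75% and every prior user attended every class, the non-user mean would be (15 × 0.75 − k)/(15 − k): 10.25/14 = 73.2% for k = 1, 9.25/13 = 71.2% for k = 2, 8.25/12 = 68.8% for k = 3, and 7.25/11 = 65.9% for k = 4. This needs a result exactly on the target together with perfect attendance by all prior users. The documents support neither assumption.

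**The case for a change.** The strongest case for acting is that the rule is ambiguous to those who must apply it, that prior users are likely to be among the candidates, and that a feasibility report should say whom its adherence figure represents. Clarifying would cost one sentence and perhaps one question. Part of this stands. The duplicate is a real slip, and the text does not explain why the caregiver rule stops at caregivers.

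The rest does not carry far. Different criteria for the two roles are not a contradiction, and admitting patients with some yoga experience is a legitimate choice in a single-arm feasibility study whose analysis is descriptive and avoids formal inference. If a later trial uses the same patient criteria, adherence that includes experienced patients is the figure it needs. Extending the exclusion to patients would buy a more uniform group at the price of screen failures in a sample of 15.

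A comparison with and without perhaps 1 to 4 patients would be too thin to alter any conclusion. A patient-only attendance advantage is also less plausible here, because the patient is treated together with a caregiver who has done no yoga for a year. Finally, the adherence hypothesis is not limited to patients. Averaged over all 30 participants, with caregivers' attendance unaffected, the shifts in step 5 halve to about 0.3 to 1.1 points for one class and 0.8 to 3.3 for three.

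**Conclusion.** The textual observation is right, but it does not call for a change to the design or analysis. The repeated line is a clerical slip. Whether the criterion also covers patients is a missing detail that the study team knows from its own screening practice and can state when it reports eligibility.

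Under the printed rule, adherence and satisfaction are sound descriptive results for the patients enrolled. The sample size and the analysis method do not depend on this point. The possible shift in mean adherence is 0.6 to 2.2 points for a one-class difference and 1.7 to 6.7 points for a three-class difference. Both ranges assume 1 to 4 prior users among 15 patients and adherence read as mean share of classes. Such a shift would matter only if the result fell close to 75%, and the documents do not indicate whether experience would raise or lower attendance.
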